Similar longitudinal modeling approaches will be applied to evaluate treatment effects on other secondary outcome variables. Appropriate models will be applied depending on the scale of the outcome variable, but the model for fixed effects/linear component will remain consistent across outcomes. For opioid use, a binary outcome, we will apply generalized estimating equations along with a logistic link function and unstructured working covariance matrix. For analgesic-related side effect frequency and severity, physical function, overall health, sleep quality, and healthcare utilization, all quantitative measures, we will compare mean response over time by applying generalized estimating equations along with an identity link function and unstructured working covariance matrix. All comparisons will be made using appropriately specified linear contrasts, tested at the 5% significance level, and/or 95% confidence intervals.

Non-opioid analgesic use and use of other pain management strategies will be descriptively summarized by randomization group and time, without any plans to apply inferential statistical methods (hypothesis tests or confidence intervals).

Exploratory Analyses: To assess whether some groups of participants are more likely to benefit from the interventions, we will estimate and compare effects using tests of interaction for a priori identified subgroups based on gender, race, health literacy, access to a PCP, and preference for control over decision-making⁴. To assess for potentially differential intervention effects on the primary outcome across each of the subgroups, we will use ANCOVA models similar to that for the primary analysis, but with the addition of appropriate interactions between intervention groups and subgroups. Separate models will be used to assess each interaction. Interpretation of differential effects of the intervention will be limited to subgroups for which an interaction is significant at the 5% level.

⁴ After enrollment was converted to remote due to COVID, which meant that the intervention was experienced following the ED visit, the shared decision making items were dropped from the study. Thus, we will not use “preference for control over decision-making” as a variable in our models.

11. Assessing Potential Mechanisms (Objective 2)

To address the Objective 2, we will apply structural equation models (specifically, longitudinal path analyses with manifest variables) with all variables incorporated appropriately for their scale. The structural equation models will be fit using MPlus software, version 8.3 or higher. The models will use data from all participants and will control for the same baseline variables as for the primary objective. Full maximum likelihood methods will be used, which allow for inclusion of all observed data for participants who contribute incomplete data. The primary model will include direct and indirect effects from the interventions to the longitudinal outcomes through potential mediating variables (self-efficacy and other “process-related” variables measured at the 1-week phone call) to allow for assessment of whether mediation is present, and if so, whether it is complete or partial. No structural relationships will be imposed relating the potential mediating variables to one another, beyond simple correlations. For the longitudinal outcomes, we will include Pain Severity and Interference in the model as separate variables, which we will allow to be correlated at each time point. We will first test each of the path coefficients from the interventions to the mediator variables separately at the $p=0.05$ level using chi-squared difference tests. We will then test indirect paths to assess mediation. We will compare full and reduced models (with selected paths restricted to be zero) using chi-squared difference tests. Standard model fit indices (i.e., RMSEA, Bollen’s incremental index, and the Tucker-Lewis index) will be reported.

A schematic diagram of the general model set up is shown in Figure 1 below. In this figure, straight arrows represent structural paths, curved arrows represent correlations.

12. Summary of Safety Data

Adverse events will be descriptively summarized for the ITT Population, by randomized treatment group, using frequency tables. Summaries will also be presented according to severity and perceived relatedness to the study. No inferential statistics (hypothesis tests or confidence intervals) will be presented for comparing across groups.

Figure 1. Schematic diagram of the proposed longitudinal path model.

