### **Usual Care**

Patients randomized to the usual care arm will receive education, prescriptions, and advice on recovery promoting behaviors as typically provided by medical providers. We have chosen not to include a sham intervention or enhanced usual care because the intent of the study is to determine if the intervention improves upon what is typically done for these patients. Consistent with this intent, no restrictions will be placed on the care from providers for any of the study arms.

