Enrolled participants will complete a baseline assessment in the ED/Urgent Care or remotely by phone¹, a phone call at 1 week to assess processes that might mediate recovery, and phone calls at 1, 3, 6, and 12 months to assess outcomes.

ClinicalTrials.gov Identifier: NCT04118595

¹ Due to the COVID-19 pandemic, all study operations were successfully converted to remote operations between March 12th and April 8th, which received IRB approval on April 8, 2020. On April 13th, screening and enrollment by phone re-started and has continued without interruption. Since April, all study activities including recruitment, enrollment, intervention delivery, and follow-up calls have been conducted by study personnel remotely.

3. Analysis Populations

Two analysis populations will be defined for this study:

- *Intention-to-Treat (ITT) Population:* This population will include all participants who were randomized, analyzed according to the group to which they were randomized. Nobody will be excluded, regardless of treatment actually received.
- *Per-Protocol Population:* This population will be a subset of the ITT population and will exclude all participants who were found to meet exclusionary criteria after enrolling in the study, specifically patients who are admitted to the hospital and patients who are found to have pain that is not musculoskeletal in origin. The Per-Protocol population will also exclude participants who did not receive their intended treatment (i.e., participants in Groups 1 or 2 who viewed less than 50% of the video or watched the video more than 24 hours after visit, and participants in Group 1 who were not reached for the telecare call).

4. Unblinding Plan

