As an open-label study, participants, providers, and many study staff will know to which group individual participants have been randomized (the Research Assistants who conducted the follow-up interviews were blinded to treatment arm assignment). However, efforts will be made to keep the principal study statistician blinded to randomization group during the course of the trial. Any key decisions regarding study outcomes, the appropriateness of test statistics or model assumptions, changes to this analysis plan, or any other statistical issues will be made in a blinded review of the data (i.e., blinded to the true randomization groups). The generated allocation sequence has been generated by the Lead Data Manager and uploaded to the secure REDCap randomization module. Datasets provided to the principal statistician prior to unblinding will not include randomized treatment assignment. Primary ITT analyses will be initially programmed using dummy (computer generated) treatment assignments. Unblinding with respect to the true randomization groups will only be done for the final interpretation of the results. Membership in the Per-Protocol Population cannot be adjudicated without knowing actual group assignment.

5. Scoring of Outcome Variables and Certain Baseline Control Variables

Many outcome variables and some baseline control variables will be measured using validated scales or indices. The scoring to be used for each of these scales/indices, including handling of missing scale items, is described in this section.

a. The Brief Pain Inventory Short Form (BPI-SF)

The BPI-SF is composed of two sub-scales, one for pain severity and the other for interference. Pain severity is measured using four items to assess pain at its “worst in the past week”, “least in the past week”, “average in the past week”, and “right now”. Each of these is scored on a 0 to 10 scale, with 0 indicating “none” and 10 indicating “worst”. A Pain Severity Score will be obtained using the mean of these four items. If at most one of the four items is missing, we will use item-mean imputation and take the mean of the 3 non-missing items.

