For each outcome measured using a scale, missing scale items will be imputed as described in Section 5 above. Data missing by design (e.g., due to a skip pattern in the data collection form) will be filled in logically where appropriate.

7. Analysis of Participant Follow-Up

We will present an account of the final disposition (completed, withdrew, lost, or died) for each participant in the ITT Population, including any admission violations and group assignment. The number and proportion of participants in the ITT population who provided information for the analyses of the study objectives will be summarized by randomization group. Frequencies of participants with missing primary outcome data will be summarized by randomization group and study visit. We will provide a CONSORT diagram showing the flow of participants through the trial, indicating withdrawals by treatment arm with reasons, when provided.

8. Analysis of Baseline Data

We will summarize baseline data (i.e., pre-randomization data) for the ITT Population, by randomization group, site type (ED vs. Urgent Care), and overall. Measures of central tendency and dispersion for continuous and certain discrete variables will include means, standard deviations, medians, minima, and maxima. Categorical data will be summarized with frequencies and percentages. Some continuous variables may also be grouped into categorical levels and evaluated in frequency tables. No inferential statistics (i.e., p-values and/or confidence intervals) for comparing data between groups will be presented.

9. Primary Analysis of Primary Outcome (Objective 1)

The primary analysis of BPI-SF will use the ITT Population, and will be repeated secondarily using the Per-Protocol Population. We will use a linear mixed model to conduct an analysis of covariance (ANCOVA), controlling for site type (ED vs. Urgent Care), baseline pain severity, age, gender, race,

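### The per-protocol exclusions for non-receipt fall only on the intervention arms, so the per-protocol contrasts can be biased in either direction and should not be read as treatment effects

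*SAP*

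**What the plan says.** SAP section 3 builds the per-protocol population in two steps. The first removes patients found ineligible after enrolment, "specifically patients who are admitted to the hospital and patients who are found to have pain that is not musculoskeletal in origin". This step applies to every arm.

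The second step is introduced by "The Per-Protocol population will also exclude participants who did not receive their intended treatment". The SAP defines it by two rules. The video rule covers both intervention arms: "participants in Groups 1 or 2 who viewed less than 50% of the video or watched the video more than 24 hours after visit". The telecare rule covers the full arm alone and removes "participants in Group 1 who were not reached for the telecare call". Group 1 is the full intervention and Group 2 is video-only. No rule is given for Group 3, and the Protocol's description of that arm explains why: "Patients randomized to the usual care arm will receive education, prescriptions, and advice on recovery promoting behaviors as typically provided by medical providers".

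SAP section 4 confirms that the population depends on arm: "Membership in the Per-Protocol Population cannot be adjudicated without knowing actual group assignment". SAP section 9 fixes the role of the analysis: "The primary analysis of BPI-SF will use the ITT Population, and will be repeated secondarily using the Per-Protocol Population". The repeat uses the same mixed model, the same covariates and the same contrasts of each intervention arm with control. Neither document plans a correction for selection on receipt, such as weighting or a complier-average estimate.

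**The concern.** Watching half a video within a day, or being reached by a nurse, is behaviour after randomisation. The SAP observes it and filters on it in the intervention arms only. The usual-care patients who would not have watched, or would not have been reached, cannot be identified and stay in. The per-protocol contrasts with usual care therefore lose the protection of randomisation. The full arm passes through two filters and the video-only arm through one, so the comparison between them is affected as well.

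If receivers and non-receivers differ in pain outlook in ways the covariates do not capture, the per-protocol contrast departs from zero even when neither intervention does anything. It could then be taken as support for, or against, the primary result.

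**Working it through.** **The plan's own figures.** Protocol section 6.2 inflates 120 per arm for up to 10% admissions: 360 / (1 − 0.10) = 400, which reproduces. The means and covariances behind the power statement are in figures not available here, so only its consistency can be checked. For a 3 df test at 2.5%, 93% power needs a noncentrality of 18.1. Scaling by (15/20)² = 0.5625 gives 10.2 and a power of 67.7% for video-only (stated: 67%). The 6 df overall test comes out at 93.5% (stated: at least 90%). The plan's figures agree with each other, but the inflation covers admissions only and makes no allowance for non-receipt.

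**Exclusions by arm (SAP section 3).**

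| Rule | Full | Video-only | Usual care |
|---|---|---|---|
| Admitted to hospital | yes | yes | yes |
| Non-musculoskeletal pain | yes | yes | yes |
| Video under 50% or late | yes | yes | no |
| Not reached for telecare | yes | no | no |

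**Shift with no true effect.** Let q be the share of an intervention arm removed for non-receipt. Let D be mean pain in non-receivers minus mean pain in receivers, after covariate adjustment. The whole-arm mean is the receivers' mean plus q × D. Usual care has the same mix but is unfiltered, so the per-protocol contrast (intervention minus usual care) is −q × D. It is zero only if D = 0, and it changes sign with D.

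The documents give neither q nor D, so the following are assumptions:

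- Video rule alone, q = 20%: 0.20 × 0.5 = 0.10 and 0.20 × 1.0 = 0.20 points.
- Full arm, with a further 10% lost at telecare: q = 1 − 0.8 × 0.9 = 28%, giving 0.14 to 0.28 points.
- Full versus video-only, same D: (0.28 − 0.20) × D = 0.04 to 0.08 points.

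For scale, the planned video-only effect is 15% of the usual-care mean. If that mean is 4 (an assumption), the effect is 0.6 points, and a shift of 0.10 to 0.20 is 17% to 33% of it.

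**Effect on error rate.** This assumes 120 usual-care patients, 120 × (1 − q) in the intervention arm, a constant shift over three visits, SD 2.0 to 3.0 and between-visit correlation 0.5 to 0.7. The nominal 2.5% error of one 3 df contrast, ignoring the overall gate, becomes:

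| q | D = 0.5 | D = 1.0 |
|---|---|---|
| 10% | 2.6–2.7% | 2.8–3.3% |
| 20% | 2.8–3.2% | 3.6–5.8% |
| 30% | 3.1–4.1% | 5.0–10.4% |

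**Simulation without a treatment effect** (SD 2.5, no covariates, q = 20%). When the tendency to receive is correlated 0.2 with outcome, the one-sided per-protocol contrast is −0.181. The intention-to-treat contrast is −0.006, and a contrast restricted to would-be receivers in both arms is −0.008. With zero correlation all three are close to zero.

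**Price of the alternative.** If nobody in usual care receives the video, a complier-average estimate is essentially the intention-to-treat difference divided by the receipt rate. At 80% receipt and about 133 per arm, its standard error is proportional to √(2/133) / 0.80 = 0.153. The per-protocol value is √(1/120 + 1/96) = 0.137. The interval is about 12% wider (0.153 / 0.137 = 1.12).

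**The case against.** The strongest reply is that little depends on this analysis. Intention-to-treat is primary and excludes nobody, the per-protocol repeat is secondary, and no gate or significance level rests on it. Any per-protocol comparison against an untreated control has this weakness. That stands, and it limits the importance of the point.

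Several stronger readings are tempting, and the documents do not support them:

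- *That receivers are compared with every usual-care patient.* Usual care also loses admitted and non-musculoskeletal patients.
- *That the analysis is biased, and in favour of the interventions.* Bias requires receipt to be prognostic after adjustment. Patients who recover quickly may also skip a video or a call, which would push the contrast the other way.
- *That the covariates miss what drives receipt.* The documents do not say what drives it. The model includes site type, baseline pain, age, gender, race, comorbidity, opioid use, chronic pain history and access to a primary care provider, and some of these may predict engagement. Protocol section 5.2 also collects literacy, social support, self-efficacy, depression and anxiety, which the model omits. So adequate adjustment is neither shown nor ruled out.
- *That the per-protocol analysis is the plan's designated estimate of the effect of receipt.* Neither document gives it that role. Protocol section 6.2 even describes it as limited to non-admitted patients, which is neutral between arms.

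There is also a fair objection to the remedy. A complier-average estimate largely rescales intention-to-treat and needs the exclusion restriction: assignment must affect pain only through receipt. In an open-label trial with self-reported pain that is open to doubt. A strict definition of receipt strains it further, because patients who saw part of the video, or the video without telecare, would count as untreated. This stands, and the definitions proposed under the fix are chosen to reduce it.

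**Conclusion.** The point holds as a cheap improvement to a secondary analysis. The one-sided filter is plain on the text of SAP section 3, and neither document plans a correction. The resulting contrasts can be biased either way, while the primary intention-to-treat analysis is not affected.

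The size is illustrative: 0.10 to 0.20 BPI points at 20% excluded and a residual gap of 0.5 to 1.0 points. It is smaller where the covariates absorb part of the gap, zero if receipt is not prognostic, and reversed if non-receivers do better. The documents supply no non-receipt rate, prognosis gap, SD or usual-care mean. The figures therefore show what is possible and do not estimate what will happen. Because the sign is unknown, the per-protocol result should not be interpreted as a treatment effect.

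**What to change.** 1. State in SAP sections 3 and 9 that the per-protocol comparison with receipt exclusions is descriptive and does not estimate a treatment effect.
2. Add a complier-average estimate of the effect of receipt in the intention-to-treat population, with randomised arm as instrument and the same outcomes and covariates. Using the whole randomised population avoids applying the instrument to a set already selected after randomisation.
3. Define receipt leniently: any video viewed, at any time, for video-only; any component received for the full arm. Use the 50% viewing threshold only as a sensitivity analysis.
4. State the assumptions: the exclusion restriction, and that usual-care patients have no access to the video. The second is reasonable, since Protocol sections 4.3 and 4.4 send the link only to those randomised to it, but it should be written down.
5. While editing, reconcile the differing per-protocol definitions in Protocol sections 3.4, 4.4, 6.1 and 6.2 with SAP section 3.

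The cost is SAP wording and one extra model. The SAP's own exclusions already presuppose records of viewing and telecare contact; confirm that they can identify any viewing as well as viewing above the threshold. The downsides are a wider interval and reliance on the exclusion restriction in an open-label trial with self-reported pain.

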#### 4.6 Withdrawal procedures

Subjects may withdrawal from the study at any time. If such a request is made, no further contact with the subject will be made. Data that was collected prior to withdrawal will be retained unless the subject requests that all data be removed from the study.

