The Gagne Comorbidity Score will be calculated based on baseline data. The weights indicated below will be applied to each item, as detailed here: <https://scholar.harvard.edu/gagne/software/combined-comorbidity-score> .

```

if disease = 'metastatic_romano' then weight = 5;
if disease = 'chf_romano' then weight = 2;
if disease = 'dementia_romano' then weight = 2;
if disease = 'renal_elixhauser' then weight = 2;
if disease = 'wtloss_elixhauser' then weight = 2;
if disease = 'hemiplegia_romano' then weight = 1;
if disease = 'alcohol_elixhauser' then weight = 1;
if disease = 'tumor_romano' then weight = 1;
if disease = 'arrhythmia_elixhauser' then weight = 1;
if disease = 'pulmonarydz_romano' then weight = 1;

```

```

if disease = 'coagulopathy_elixhauser' then weight = 1;
if disease = 'compdiabetes_elixhauser' then weight = 1;
if disease = 'anemia_elixhauser' then weight = 1;
if disease = 'electrolytes_elixhauser' then weight = 1;
if disease = 'liver_elixhauser' then weight = 1;
if disease = 'pvd_elixhauser' then weight = 1;
if disease = 'psychosis_elixhauser' then weight = 1;
if disease = 'pulmcirc_elixhauser' then weight = 1;
if disease = 'hivaids_romano' then weight = -1;
if disease = 'hypertension_elixhauser' then weight = -1;

```

6. Missing Outcome Data, Out of Window Visits, and Sensitivity Analyses

Missing data for the primary outcome will be ignored (treated as missing at random) in the primary ITT analysis. For the 1-, 3-, and 6-month visits, outcomes for any visits that fall outside the ± 7 day window will be set to missing for the primary analysis (with time computed as follow-up call date minus enrollment date). However, as a first sensitivity analysis, we will repeat the primary analysis using all observed data even if the visits fall outside the visit window. This analysis will repeat the same comparison of mean BPI-SF scores at 30, 90, and 180 days, but time will be treated continuously in this model and actual visit dates will be used. As a second sensitivity analysis, we will repeat the primary analysis using multiple imputation to account for any missing BPI-SF scores. The multivariate normal multiple imputation method will be used, and imputations will be based on all of the control variables included in the primary model.

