comorbidity score, baseline intermittent opioid use, a history of chronic pain, and access to a PCP (access to a PCP was used to stratify the randomization and, as such, it is important to control for it in all models). These control variables were selected a priori based on prior evidence of prognostic value and will not be subjected to significance testing. This model will include all pain severity scores (1, 3, 6, and 12 months) as outcomes; will include fixed effects for group, visit, and group-by-visit; and will use an unstructured covariance matrix for the error terms. We will first test a 6 degrees of freedom (df) linear contrast of the overall null hypothesis of no mean difference in the primary outcome at any of the 1-, 3-, and 6-month follow-up assessments across the 3 groups at the 5% significance level. If the overall null hypothesis is rejected, we will then conduct two separate 3 df contrasts to compare each of the intervention groups with the control group using a Bonferroni-adjusted 2.5% significance level. We will secondarily estimate mean pairwise differences along with 95% confidence intervals at each time point, including data collected at the 12-month follow-up time point.

10. Secondary and Exploratory Analyses (Objective 1)

The same linear mixed modeling approach used for the primary outcome will be applied to each of the separate components of the BPI-SF (Pain Severity and Interference). Similar comparisons using the sequence of linear contrasts and 95% confidence intervals as specified for the primary outcome will be made.

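### The planned multiple imputation makes the same missing-at-random assumption as the primary model, so their agreement cannot show that the result withstands informative withdrawal or loss

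*SAP*

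**What the plan says.** SAP section 6 sets the rule for the primary analysis: "Missing data for the primary outcome will be ignored (treated as missing at random) in the primary ITT analysis". The model in SAP section 9 is a linear mixed model that "will use an unstructured covariance matrix for the error terms", so it is a likelihood analysis that is valid under that assumption.

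Two sensitivity analyses follow.

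- Out-of-window scores: "as a first sensitivity analysis, we will repeat the primary analysis using all observed data even if the visits fall outside the visit window". Time becomes continuous. Nothing is done about scores that were never obtained.
- Missing scores: "As a second sensitivity analysis, we will repeat the primary analysis using multiple imputation to account for any missing BPI-SF scores". The method is multivariate normal, and "imputations will be based on all of the control variables included in the primary model".

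SAP section 7 adds descriptive tables: each participant's final status, missing primary data by arm and visit, and withdrawals by arm with reasons. Protocol 6.1 adds loss rates by arm and a baseline comparison of those who did and did not complete follow-up. It also describes an imputation with more predictors, but that one is aimed at patients taking analgesics, and the SAP says that it replaces the protocol's summary plan.

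On the setting, SAP section 4 states: "As an open-label study, participants, providers, and many study staff will know to which group individual participants have been randomized". Follow-up interviewers are blinded. Under Protocol 4.6, once a participant withdraws, "no further contact with the subject will be made".

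**The concern.** A sensitivity analysis for missing data is informative when it changes the assumption that the data cannot test. Here the assumption is that, given the covariates, arm and earlier scores, people whose scores are unseen have the same pain as similar people whose scores are seen. The imputation keeps that assumption and adds no new information about the missing scores.

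The setting gives reason to test it. The outcome is self-reported pain, participants know what they were assigned, and scores after withdrawal cannot be recovered. If people who did not benefit left one arm more than another, the primary analysis and the imputation would both carry the error. Their agreement could then be reported as robustness to dropout that neither analysis had examined.

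**Working it through.** **Inputs.** From Protocol 6.2: exponential loss reaching 20% at 12 months; 120 per arm for the power statement; post-randomization means 20% (full) and 15% (video-only) below usual care; power of 93% and 67% for 3-df tests at 2.5%. Enrolment is 400, about 133 per arm. The means and covariance matrix behind the power are in figures not shown, so the visit correlation and SD below are assumptions.

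**1. Check the stated powers against each other.** With a chi-square on 3 df at 2.5% (critical value 9.35), 93% power needs noncentrality 18.09. Scaling by (15/20)² gives 18.09 × 0.5625 = 10.18, hence 67.7% power, against 67% stated. The two figures agree.

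**2. Planned loss by visit.** Loss at month t is 1 − 0.8^(t/12): 1.8% at 1 month, 5.4% at 3 months and 10.6% at 6 months. The last is 0.106 × 133 ≈ 14 people per arm. Out-of-window scores set to missing come on top.

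**3. Bias if one arm's unseen scores are worse.** If they are worse by δ than the model predicts, the 6-month difference is off by about 0.106 × δ:

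- δ = 0.5 SD: 0.05 SD
- δ = 1 SD: 0.11 SD

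With equal loss and equal δ in both arms, the error cancels.

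**4. Put this against the planned video-only effect.** Power of 67% needs noncentrality 10.05, so √(2 × 10.05/120) = 0.41. This is a multivariate distance over three visits. With a constant effect and common correlation ρ, the per-visit effect is 0.41/√(3/(1 + 2ρ)):

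- ρ = 0.4: 0.32 SD
- ρ = 0.6: 0.41/√(3/2.2) = 0.35 SD
- ρ = 0.8: 0.38 SD

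At ρ = 0.6 the bias is 0.053/0.35 ≈ 15% and 0.106/0.35 ≈ 30% of the effect. Removing the 6-month effect entirely needs 0.35/0.106 ≈ 3.3 SD.

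**5. What a shift does to the 3-df test.** Take 133 per arm, ρ = 0.6, per-visit effect e (0.35 SD video-only; 0.47 SD full, by the same formula) and loss vector m = (0.018, 0.054, 0.106). The noncentrality is (133/2)(e − δm)′R⁻¹(e − δm), where R is the correlation matrix. This ignores the information lost through missing data, so it is a guide only.

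| δ (SD), intervention arm only | Video-only: noncentrality (power) | Full: noncentrality (power) |
|---|---|---|
| 0 | 11.1 (72%) | 20.1 (95%) |
| 0.5 | 9.5 (64%) | 17.8 (92%) |
| 1 | 8.3 (57%) | 15.9 (89%) |
| 2 | 7.4 (51%) | 13.7 |
| 4 | 11.4 (74%) | 15.1 |

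The noncentrality falls and then rises. The shift grows with loss across visits, so a large δ makes the arms differ in shape over time, which the 3-df test also detects.

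**6. Does imputation expose the error?** An illustrative simulation assumed no true effect, SD 2.5, 133 per arm and about 20% missing at 6 months. Loss in the full arm depended on the person's own unseen score; usual-care loss was random. Over 60 runs the 6-month difference in points was +0.09 with complete data, −0.24 by likelihood and −0.22 by multiple imputation (simulation standard error 0.04). Both methods carry a false benefit of about 0.3 points.

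**The case against.** Missing at random with a mixed model is a defensible primary analysis, and the plan is not silent on loss. The first sensitivity analysis recovers scores that the primary analysis discards, and the descriptive tables could reveal unequal loss. That stands, but none of these estimates what informative loss would do to the treatment difference.

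A reader might infer three stronger points, and the documents do not support them.

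- **That the imputation must reproduce the primary result.** The SAP does not say that treatment group is in the imputation model; read literally, control variables leave it out, whereas Protocol 6.1 names it. If group is omitted, imputed differences between arms shrink and the two analyses may disagree. That disagreement would say nothing about informative loss either.
- **That the trial will overstate benefit.** One-sided loss is a scenario, not a finding. Participants' knowledge of their arm does not establish it, follow-up interviewers are blinded, equal loss with equal δ cancels, and worse unseen scores in usual care would understate the benefit. The documents report no observed loss.
- **That dropout could easily overturn the result.** At planned loss it could not remove the effect without a very large shift. The usual-care 6-month mean is not shown; if it is 2 to 5 points, bringing the 6-month difference to zero needs 2.8 to 7.1 points for video-only and 3.8 to 9.5 for full.

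The 0.41 in step 4 should likewise not be read as a 6-month difference.

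**Conclusion.** The point holds as a limit on what may be claimed. The planned analyses share one untestable assumption about withdrawal and loss, and neither document contains an analysis that departs from it. Their agreement would not be evidence of robustness to informative dropout.

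At planned loss the size is moderate: 0.05 to 0.11 SD at 6 months for a one-arm shift of 0.5 to 1 SD, or about 15% to 30% of the implied video-only effect. This rests on the protocol's loss model, a constant effect and an assumed visit correlation of 0.6. The video-only comparison is the more exposed, because its planned power is only 67%. The full-intervention comparison is much less sensitive unless loss is higher than planned or differs by arm. The primary analysis need not change; this is a worthwhile, inexpensive addition.

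**What to change.** Amend SAP section 6, before unblinding, as follows.

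1. Keep the planned imputation and state that treatment group is in the imputation model.
2. Add a delta adjustment. After imputation, shift upward the imputed scores of those who withdrew or were lost, first in the intervention arms only and then in all arms. Use a grid such as 0 to 2 points in steps of 0.5, extended until the conclusion changes or the limit of the 0–10 scale is reached. With an SD of 2 to 2.5 points (assumed), 2 points is only 0.8 to 1 SD, which step 5 suggests would probably not tip the full-intervention comparison.
3. At each delta, report the 1-, 3- and 6-month differences with confidence intervals, and the 3-df p-value for each comparison with usual care. Since that test need not weaken steadily as delta grows, it may never lose significance; if so, say so.
4. State how scores after death are handled.

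This needs no new data: the status recorded under SAP section 7 identifies whose scores to shift. The cost is SAP wording, a few lines in the imputation program and one more table.
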